3.3.3 Women of Childbearing Potential

A woman of childbearing potential (WOCBP) is defined as any female who has experienced menarche and who has not undergone surgical sterilization (hysterectomy or bilateral oophorectomy) and is not postmenopausal. Menopause is defined as 12 months of amenorrhea in a woman over age 45 years in the absence of other biological or physiological causes. In addition, females under the age of 55 years must have a serum follicle stimulating hormone, (FSH) level > 40 mIU/mL to confirm menopause.

Females treated with hormone replacement therapy (HRT) are likely to have artificially suppressed FSH levels and may require a washout period in order to obtain a physiologic FSH level. The duration of the washout period is a function of the type of HRT used. The durations of the washout period below are suggested guidelines and the investigators should use their judgment in checking serum FSH levels. If the serum FSH level is >40 mIU/mL at any time during the washout period, the woman can be considered postmenopausal:

1 week minimum for vaginal hormonal products (rings, creams, gels)

4 week minimum for transdermal products

8 week minimum for oral products

Other parenteral products may require washout periods as long as 6 months.

[REDACTED]

[REDACTED]

[REDACTED]

[REDACTED]

[REDACTED]

[REDACTED]

[REDACTED]

[REDACTED]

[REDACTED]

[REDACTED]

[REDACTED]

[REDACTED]

3.5 Discontinuation of Subjects Following Any Treatment with Study Drug

Subjects MUST discontinue investigational product (and non-investigational product at the discretion of the investigator) for any of the following reasons:

- Subject's request to stop study treatment
- Any clinical adverse event (AE), laboratory abnormality or intercurrent illness which, in the opinion of the investigator, indicates that continued participation in the study is not in the best interest of the subject
- Pregnancy
- Termination of the study by Bristol-Myers Squibb (BMS)
- Loss of ability to freely provide consent through imprisonment or involuntarily incarceration for treatment of either a psychiatric or physical (eg, infectious disease) illness
- Second malignancy requiring systemic anticancer treatment

In the case of pregnancy, the investigator must immediately notify BMS Medical Monitor/designee of this event. In most cases, the study drug will be permanently discontinued in an appropriate

manner. If the investigator determines a possible favorable benefit/risk ratio that warrants continuation of study drug, a discussion between the investigator and the BMS Medical Monitor/designee must occur.

All subjects who discontinue investigational product should comply with protocol-specified follow-up procedures as outlined in [Section 5](#). The only exception to this requirement is when a subject withdraws consent for all study procedures including post-treatment study follow-up or loses the ability to consent freely (ie, is imprisoned or involuntarily incarcerated for the treatment of either a psychiatric or physical illness).

If study treatment is discontinued prior to the subject's completion of the study, the reason for the discontinuation must be documented in the subject's medical records and entered on the appropriate case report form (CRF) page.

3.6 Post-Study Drug Study Follow up

Subjects who discontinue study treatment may continue to be followed. In this study, safety and survival are key endpoints of the study. Post-study follow-up is of critical importance and is essential to preserving subject safety and the integrity of the study. Subjects who discontinue study drug must continue to be followed for collection of outcome and/or survival follow-up data as required and in line with [Section 5-Study Assessments and Procedures--until death or the conclusion of the study](#).

The subjects will be followed up for select AEs for a minimum of 100 days from the last dose of study therapy and for ongoing drug-related AEs until resolved, return to baseline or deemed irreversible, or until lost to follow-up or withdrawal of study consent.

One of the endpoints is overall survival, and every attempt will be made to obtain survival status every 3 months or until death, lost to follow-up, withdrawal of study consent, or end of study.

3.6.1 Withdrawal of Consent

Subjects who request to discontinue study drug will remain in the study and must continue to be followed for protocol-specified follow-up procedures. The only exception to this is when a subject specifically withdraws consent for any further contact with him/her or persons previously authorized by the subject to provide this information. Subjects should notify the investigator of the decision to withdraw consent from future follow-up **in writing**, whenever possible. The withdrawal of consent should be explained in detail in the medical records by the investigator, as to whether the withdrawal is from further treatment with study drug only or also from study procedures and/or post-treatment study follow-up, and entered on the appropriate CRF page. In the event that vital status (whether the subject is alive or dead) is being measured, publicly available information should be used to determine vital status only as appropriately directed in accordance with local law.

3.6.2 Lost to Follow-Up

All reasonable efforts must be made to locate subjects to determine and report their ongoing status. This includes follow-up with persons authorized by the subject as noted above. Lost to follow-up

is defined by the inability to reach the subject after a minimum of 3 documented phone calls, faxes, or emails as well as lack of response by subject to 1 registered mail letter. All attempts should be documented in the subject's medical records. If it is determined that the subject has died, the site will use permissible local methods to obtain the date and cause of death.

If investigator's use of third-party representative to assist in the follow-up portion of the study has been included in the subject's informed consent, then the investigator may use a Sponsor-retained third-party representative to assist site staff with obtaining subject's contact information or other public vital status data necessary to complete the follow-up portion of the study. The site staff and representative will consult publicly available sources, such as public health registries and databases, in order to obtain updated contact information. If after all attempts, the subject remains lost to follow-up, then the last known alive date as determined by the investigator should be reported and documented in the subject's medical records.

4 TREATMENTS

4.1 Study Treatments

Study drug includes both Investigational [Medicinal] Product (IP/IMP) and Non-investigational [Medicinal] Product (Non-IP/Non-IMP) and can consist of the following:

- All products, active or placebo, being tested or used as a comparator in a clinical trial
- Study-required premedication
- Other drugs administered as part of the study that are critical to claims of efficacy (eg, background therapy, rescue medications)
- Diagnostic agents (such as glucose for glucose challenge) given as part of the protocol requirements must also be included in the dosing data collection.

[REDACTED]	[REDACTED]	[REDACTED]	[REDACTED]	[REDACTED]
[REDACTED]	[REDACTED]	[REDACTED]	[REDACTED]	[REDACTED]
[REDACTED]	[REDACTED]	[REDACTED]	[REDACTED]	[REDACTED]
[REDACTED]	[REDACTED]	[REDACTED]	[REDACTED]	[REDACTED]

[REDACTED] [REDACTED]

4.6.1 Management of Select Adverse Events

In some cases, the natural history of AEs associated with immunotherapy can differ from and be more severe than AEs caused by agents belonging to other therapeutic classes. Early recognition and management may mitigate severe toxicity. Evaluation and management guidelines for the following groups of AEs were developed to assist investigators and can be found in the Investigator Brochure:

- Pulmonary toxicity
- Gastrointestinal toxicity (diarrhea or colitis)
- Endocrinopathies
- Hepatotoxicity (including asymptomatic LFT elevations)
- Renal toxicity
- Skin toxicity
- Neurological toxicity

For subjects expected to require more than 4 weeks of corticosteroids or other immunosuppressants to manage the AE, consider the recommendations provided in the Investigator Brochure. Tumor assessments for all subjects should continue as per local standard of care and guidelines, even if dosing is interrupted.

4.6.2 Nivolumab Dose Delay Criteria

Nivolumab administration should be delayed for the following:

- Grade 2 non-skin, drug-related adverse event, with the exception of fatigue
- Grade 2 drug-related creatinine, AST, ALT and/or Total Bilirubin abnormalities
- Grade 3 skin, drug-related adverse event
- Grade 3 drug-related laboratory abnormality, with the following exceptions
- Grade 3 lymphopenia or asymptomatic amylase or lipase does not require dose delay
- Grade ≥ 3 AST, ALT, total bilirubin will require dose discontinuation
- Any adverse event, laboratory abnormality, or intercurrent illness which, in the judgment of the investigator, warrants delaying the dose of study medication

4.6.3 Nivolumab Dose Reductions and Escalations

Nivolumab dose reductions and escalations are not permitted.

4.6.4 Criteria to Resume Treatment with Nivolumab

Subjects may resume treatment with nivolumab when the drug-related AE(s) resolve to Grade \leq 1 or baseline value, with the following exceptions:

- Subjects may resume treatment in the presence of Grade 2 fatigue
- Subjects who have not experienced a Grade 3 drug-related skin AE may resume treatment in the presence of Grade 2 skin toxicity
- Subjects with Grade 2 AST, ALT and/or Total Bilirubin Abnormalities, dosing may resume when laboratory values return to baseline and management with corticosteroids, if needed, is complete.
- Drug-related pulmonary toxicity, diarrhea, or colitis must have resolved to baseline before treatment is resumed. Subjects with persistent Grade 1 pneumonitis after completion of a steroid taper over at least 1 month may be eligible for re-initiation of treatment if discussed with and approved by the BMS Medical Monitor.

Participants with drug-related endocrinopathies adequately controlled with only physiologic hormone replacement may resume treatment after consultation with the BMS Medical Monitor (or designee). Adrenal insufficiency requires discontinuation regardless of control with hormone replacement.

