4.6.5.1 Nivolumab Dose Discontinuation

- Any Grade 2 drug-related uveitis or eye pain or blurred vision that does not respond to topical therapy and does not improve to Grade 1 severity within the re-initiation period OR requires systemic treatment
- Any Grade 3 non-skin, drug-related adverse event lasting > 7 days, with the following exceptions for laboratory abnormalities, drug-related uveitis, pneumonitis, bronchospasm, neurologic toxicity, hypersensitivity reactions, infusion reactions, and endocrinopathies:
 - Grade 3 drug-related uveitis, pneumonitis, bronchospasm, neurologic toxicity, hypersensitivity reaction, infusion reactions, and endocrinopathies
 - Grade 3 drug-related endocrinopathies, adequately controlled with only physiologic hormone replacement do not require discontinuation. Adrenal insufficiency requires discontinuation regardless of control with hormone replacement.
 - Grade 3 drug-related laboratory abnormalities do not require treatment discontinuation except:
 - Grade 3 drug-related thrombocytopenia > 7 days or associated with bleeding requires discontinuation
 - Grade ≥ 3 drug-related AST, ALT or Total Bilirubin requires discontinuation*
 - Concurrent AST or ALT $> 3 \times$ ULN and total bilirubin $> 2 \times$ ULN

* In most cases of Grade 3 AST or ALT elevation, study treatment will be permanently discontinued. If the investigator determines a possible favorable benefit/risk ratio that warrants continuation of study treatment, a discussion between the investigator and the BMS Medical Monitor/designee must occur.

- Any Grade 4 drug-related adverse event or laboratory abnormality, except for the following events which do not require discontinuation:
 - Grade 4 neutropenia \leq 7 days
 - Grade 4 lymphopenia or leukopenia or asymptomatic amylase or lipase
 - Isolated Grade 4 electrolyte imbalances/abnormalities that are not associated with clinical sequelae and are corrected with supplementation/appropriate management within 72 hours of their onset
 - Grade 4 drug-related endocrinopathy adverse events, such as, hyper- or hypothyroidism, or glucose intolerance, which resolve or are adequately controlled with physiologic hormone replacement (corticosteroids, thyroid hormones) or glucose-controlling agents, respectively, may not require discontinuation after discussion with and approval from the BMS Medical Monitor.

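### Protocol 4.6.4 and 4.6.5.1 contradict each other on drug-related glucose intolerance controlled with glucose-controlling agents: the Grade 4 exemption accepts that control, while the Grade 3 endocrinopathy exemption and the resumption rule do not

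*Protocol*

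**What the plan says.** Three protocol clauses decide what happens to a subject with a drug-related endocrinopathy.

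- **Section 4.6.5.1, Grade 3.** Endocrinopathies are in a group set apart from the rule that stops treatment for a Grade 3 non-skin event lasting more than 7 days: "Grade 3 drug-related uveitis, pneumonitis, bronchospasm, neurologic toxicity, hypersensitivity reaction, infusion reactions, and endocrinopathies". The exemption follows: "Grade 3 drug-related endocrinopathies, adequately controlled with only physiologic hormone replacement do not require discontinuation". It asks for no Medical Monitor step and does not mention glucose-controlling agents.
- **Section 4.6.5.1, Grade 4.** The exceptions include "Grade 4 drug-related endocrinopathy adverse events, such as, hyper- or hypothyroidism, or glucose intolerance, which resolve or are adequately controlled with physiologic hormone replacement", for which the text gives corticosteroids and thyroid hormones, and it continues "or glucose-controlling agents, respectively, may not require discontinuation after discussion with and approval from the BMS Medical Monitor".
- **Section 4.6.4.** The general rule allows dosing to restart once the event is back to Grade 1 or lower, or to baseline. The endocrinopathy sentence adds: "Participants with drug-related endocrinopathies adequately controlled with only physiologic hormone replacement may resume treatment after consultation with the BMS Medical Monitor (or designee". It has no grade limit and does not mention glucose-controlling agents.

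Three other rules bear on the same subject. Section 4.6.2 delays dosing for "Grade 2 non-skin, drug-related adverse event, with the exception of fatigue", for most Grade 3 drug-related laboratory abnormalities, and on the investigator's judgment. Section 4.6.5.1 states "Grade 3 drug-related laboratory abnormalities do not require treatment discontinuation except" and then lists platelet and liver findings, not glucose. It also stops treatment when an interruption exceeds 6 weeks from the previous dose. The exceptions to that are prolonged steroid tapers and, with approval, reasons unrelated to the drug.

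**The concern.** The protocol foresees drug-related glucose intolerance by name and treats it as an endocrinopathy at Grade 4. An investigator who carries that label to the Grade 3 bullet, or to the resumption rule, finds a narrower definition of control that leaves out the treatment the Grade 4 bullet accepts for it. The same event could then lead to continued dosing, an open-ended delay or permanent discontinuation, depending on its grade and on which paragraph the site applies.

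What is at stake is mainly a treatment-stopping decision for an individual subject. There is also a reporting consequence. Endocrinopathies are one of the select adverse event groups in Protocol 4.6.1, and a secondary objective is to characterise the outcome of high-grade select events. SAP 7.6.1.2 tabulates select events leading to discontinuation, and SAP 7.4.2 summarises dose delays and their reasons. If sites resolve the conflict differently, those summaries partly reflect the reading chosen.

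**Working it through.** No arithmetic applies, since no rate, interval or sample-size figure depends on these clauses. The check sets the clauses side by side by means of control.

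| Clause | Controlled with hormone replacement | Controlled with glucose-controlling agents |
|---|---|---|
| 4.6.5.1, Grade 3 endocrinopathy | Exempt; no Medical Monitor step | No exemption stated |
| 4.6.5.1, Grade 4 endocrinopathy | May be exempt, with approval | May be exempt, with approval |
| 4.6.4, endocrinopathy sentence | May resume after consultation | Not mentioned |
| 4.6.4, general rule | May resume at Grade 1 or lower, or baseline | Same |

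(Adrenal insufficiency is left aside; 4.6.4 and the Grade 3 bullet exclude it.)

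1. **Classification.** The Grade 4 bullet gives glucose intolerance as an example of an endocrinopathy adverse event. On that label, a Grade 3 event of the same kind falls under the Grade 3 endocrinopathy bullets.
2. **Grade 3 default.** The bullet listing endocrinopathies has no verb. I read it as discontinuation whatever the duration. If it meant no discontinuation, the exemption that follows for hormone-replaced endocrinopathies would have no purpose.
3. **Grade 3 against Grade 4.** In the right-hand column, Grade 4 has a conditional exemption and Grade 3 has none. In the middle column the order is reversed, because Grade 4 needs approval and Grade 3 does not.
4. **Laboratory path.** If a Grade 3 glucose event is recorded as a laboratory abnormality, 4.6.5.1 does not require discontinuation. The two records of one event therefore lead to different outcomes. Section 4.6.2 would still delay dosing, since its exceptions to the Grade 3 laboratory rule do not include glucose.
5. **Resumption.** The Grade 4 wording covers events that resolve or are controlled, so it contemplates control without resolution. An event controlled with glucose-controlling agents that remains above Grade 1 and above baseline meets neither part of 4.6.4.
6. **Time limit.** If dosing is interrupted in that state, whether by the Grade 2 delay rule as the event improves or by investigator judgment, the 6-week rule runs. Waiting for glucose control is neither a steroid taper nor a reason unrelated to the drug, so neither exception clearly applies.
7. **Endpoint.** Protocol 8.4.2.1 counts subjects who report a high-grade treatment-related select event. Such an event is counted whether the subject later resumes, waits or stops.

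**The case against.** The strongest defence is that the text already offers ways through.

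- **The laboratory clause is a written path.** Glucose is a protocol chemistry test (5.3), and the Grade 3 laboratory rule spares it. This stands in part: Grade 3 does not always force discontinuation. But Protocol 6.3 prefers clinical terms to laboratory terms, the Grade 4 bullet uses the clinical term, and the laboratory path leaves the resumption gap open.
- **Insulin could be read as hormone replacement.** The documents do not settle this. The Grade 4 bullet, however, illustrates hormone replacement with corticosteroids and thyroid hormones and lists glucose-controlling agents as a separate item. Against that, the word only in the other two clauses reads as an exclusion. Even on the generous reading, non-insulin agents stay uncovered.
- **The path to a forced stop is inferred.** This stands. Section 4.6.2 has no explicit bullet for a Grade 4 endocrinopathy, and whether a controlled event stays above Grade 1 depends on CTCAE grading that the documents do not reproduce. The 6-week stop is a possibility, not a certainty.
- **Other sources may clarify.** Section 4.6.1 places endocrinopathy management guidance in the Investigator Brochure, and nearby protocol text is redacted. Clarification there cannot be excluded, but it would not make these clauses agree with each other.
- **The sponsor's Medical Monitor limits variation between sites.** True where approval or consultation is required. The Grade 3 endocrinopathy bullet has no such step.

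**Conclusion.** The contradiction is real but narrow. It concerns drug-related glucose intolerance controlled with glucose-controlling agents. For that subset, Grade 3 lacks the exemption that Grade 4 has within the endocrinopathy clauses, and a controlled event still above Grade 1 and above baseline has no written route to resume in 4.6.4.

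A reader might infer more than the documents support:

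- That Grade 4 is in general treated more leniently than Grade 3. It is not: for hormone-replaced events Grade 4 is the stricter, and its exemption is conditional throughout.
- That a Grade 4 endocrinopathy has no route to resume. It has one on resolution to Grade 1 or lower or to baseline, and another when controlled with hormone replacement.
- That the primary result is compromised. The incidence count does not depend on what happens to dosing after the event.

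I expect few subjects to be affected, but that is a judgment. The documents give no incidence for drug-related glucose intolerance, and the sponsor's list of select-event terms (SAP 7.6.1.2) is not reproduced, so no count can be derived. The conclusion rests on reading the Grade 3 list as a discontinuation rule and on glucose-controlling agents being distinct from hormone replacement, as the Grade 4 bullet presents them.

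**What to change.** Reconcile 4.6.4 with the Grade 3 and Grade 4 endocrinopathy bullets of 4.6.5.1. The passages should state consistently:

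- whether control with glucose-controlling agents counts, both for avoiding discontinuation and for resuming;
- which clause, endocrinopathy or laboratory abnormality, governs a glucose event.

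The clinical rule is for the sponsor to choose. That includes whether a Medical Monitor step applies and of what kind: the present differences (none at Grade 3, consultation to resume, approval at Grade 4) may be deliberate and need not be made uniform.

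The cost is a wording change in the next amendment and notice to sites. It needs no extra procedures, subjects or analyses.

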4.6.5 Treatment Discontinuation Criteria

Tumor assessments for all subjects should continue as per protocol even if dosing is discontinued.

4.6.5.1 Nivolumab Dose Discontinuation

- Any Grade 2 drug-related uveitis or eye pain or blurred vision that does not respond to topical therapy and does not improve to Grade 1 severity within the re-initiation period OR requires systemic treatment
- Any Grade 3 non-skin, drug-related adverse event lasting > 7 days, with the following exceptions for laboratory abnormalities, drug-related uveitis, pneumonitis, bronchospasm, neurologic toxicity, hypersensitivity reactions, infusion reactions, and endocrinopathies:
 - Grade 3 drug-related uveitis, pneumonitis, bronchospasm, neurologic toxicity, hypersensitivity reaction, infusion reactions, and endocrinopathies
 - Grade 3 drug-related endocrinopathies, adequately controlled with only physiologic hormone replacement do not require discontinuation. Adrenal insufficiency requires discontinuation regardless of control with hormone replacement.
 - Grade 3 drug-related laboratory abnormalities do not require treatment discontinuation except:
 - Grade 3 drug-related thrombocytopenia > 7 days or associated with bleeding requires discontinuation
 - Grade ≥ 3 drug-related AST, ALT or Total Bilirubin requires discontinuation*
 - Concurrent AST or ALT $> 3 \times$ ULN and total bilirubin $> 2 \times$ ULN

* In most cases of Grade 3 AST or ALT elevation, study treatment will be permanently discontinued. If the investigator determines a possible favorable benefit/risk ratio that warrants continuation of study treatment, a discussion between the investigator and the BMS Medical Monitor/designee must occur.

- Any Grade 4 drug-related adverse event or laboratory abnormality, except for the following events which do not require discontinuation:
 - Grade 4 neutropenia \leq 7 days
 - Grade 4 lymphopenia or leukopenia or asymptomatic amylase or lipase
 - Isolated Grade 4 electrolyte imbalances/abnormalities that are not associated with clinical sequelae and are corrected with supplementation/appropriate management within 72 hours of their onset
 - Grade 4 drug-related endocrinopathy adverse events, such as, hyper- or hypothyroidism, or glucose intolerance, which resolve or are adequately controlled with physiologic hormone replacement (corticosteroids, thyroid hormones) or glucose-controlling agents, respectively, may not require discontinuation after discussion with and approval from the BMS Medical Monitor.
- Any dosing interruption lasting $>$ 6 weeks from the previous dose requires discontinuation, with the following exceptions:
 - Dosing interruptions to allow for prolonged steroid tapers to manage drug-related adverse events are allowed. Prior to re-initiating treatment in a subject with a dosing interruption lasting $>$ 6 weeks, the BMS Medical Monitor must be consulted. Tumor assessments should continue as per protocol even if dosing is interrupted
 - Dosing delays lasting $>$ 6 weeks from the previous dose that occur for non-drug-related reasons may be allowed if approved by the BMS Medical Monitor (or designee).

Any adverse event, laboratory abnormality, or intercurrent illness, which in the judgment of the Investigator, presents a substantial clinical risk to the subject with continued nivolumab dosing

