4.6.7 Treatment of Nivolumab-Related Infusion Reactions

Since nivolumab contains only human immunoglobulin protein sequences, it is unlikely to be immunogenic and induce infusion or hypersensitivity reactions. However, if such a reaction were to occur, it might manifest with fever, chills, rigors, headache, rash, pruritus, arthralgias, hypotension, hypertension, bronchospasm, or other allergic-like reactions. All Grade 3 or 4 infusion reactions should be reported within 24 hours to the study medical monitor and reported as an SAE if it meets the criteria. Infusion reactions should be graded according to NCI CTCAE (Version 4.0) guidelines.

Treatment recommendations are provided below and may be modified based on local treatment standards and guidelines, as appropriate:

For Grade 1 symptoms: (Mild reaction; infusion interruption not indicated; intervention not indicated).

Remain at bedside and monitor subject until recovery from symptoms. The following prophylactic premedications are recommended for future infusions: diphenhydramine 50 mg (or equivalent) and/or acetaminophen/paracetamol 325 to 1000 mg at least 30 minutes before additional nivolumab administrations.

For Grade 2 symptoms: (Moderate reaction requires therapy or infusion interruption but responds promptly to symptomatic treatment [eg, antihistamines, non-steroidal anti-inflammatory drugs, narcotics, corticosteroids, bronchodilators, IV fluids]; prophylactic medications indicated for ≤ 24 hours).

Stop the nivolumab infusion, begin an IV infusion of normal saline, and treat the subject with diphenhydramine 50 mg IV (or equivalent) and/or paracetamol 325 to 1000 mg (acetaminophen); remain at bedside and monitor subject until resolution of symptoms. Corticosteroid or

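### Protocol 4.6.5.1: the first exception to the Grade 3 stop rule lists seven event types but omits the action, and two of them have no explicit Grade 3 stop rule elsewhere

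*Protocol*

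**What the plan says.** Protocol 4.6.5.1 lists the reasons for stopping nivolumab. The Grade 3 rule opens: "Any Grade 3 non-skin, drug-related adverse event lasting > 7 days, with the following exceptions". The same sentence goes on to name laboratory abnormalities and seven clinical event types as the excepted items. Three sub-bullets follow.

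- The first consists only of this: "Grade 3 drug-related uveitis, pneumonitis, bronchospasm, neurologic toxicity, hypersensitivity reaction, infusion reactions, and endocrinopathies".
- The second states its action: "Grade 3 drug-related endocrinopathies, adequately controlled with only physiologic hormone replacement do not require discontinuation". It adds that adrenal insufficiency does require stopping.
- The third says that Grade 3 laboratory abnormalities do not require stopping, with listed exceptions. One of these reads "Grade 3 drug-related thrombocytopenia > 7 days or associated with bleeding requires discontinuation".

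Three other provisions bear on the same events.

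- Uveitis has a rule one grade lower in the same section, "Any Grade 2 drug-related uveitis or eye pain or blurred vision that does not respond to topical therapy", which also requires failure to improve to Grade 1 in time, or else a need for systemic treatment.
- Grade 4 events have their own rule, "Any Grade 4 drug-related adverse event or laboratory abnormality, except for the following events which do not require discontinuation".
- Protocol 4.6.7 permanently stops nivolumab after a Grade 3 or 4 infusion reaction.

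**The concern.** This is an operative safety rule, and its wording allows two opposite actions for the seven listed types.

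- **Stop at any duration.** The exception removes only the 7-day condition, so nivolumab stops at once.
- **Exempt.** The exception removes the event from the stop rule, so nivolumab may restart after resolution.

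The second is the ordinary meaning of an exception to a stop rule. On that meaning, Grade 3 colitis lasting more than 7 days stops treatment and Grade 3 pneumonitis lasting more than 7 days does not. That ordering is implausible in a study whose purpose is to characterise such events. Two sites could handle the same pneumonitis or neurologic event differently, and one of them would re-expose the subject.

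**Working it through.** The plan states no figure on this point, so the check is a comparison of texts and a count.

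**Step 1: which reading is intended?** Outside the disputed line, 4.6.5.1 has five entries that are bare phrases and mean *stop*: the Grade 2 uveitis rule, the Grade 3 parent rule, concurrent transaminase and bilirubin elevation, the Grade 4 parent rule, and the investigator-judgment rule. Three bare phrases in the Grade 4 list mean *exempt*, but their lead-in says so. The Grade 3 lead-in says only that exceptions follow. Three further facts point to *stop*:

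- The section concerns discontinuation.
- The second sub-bullet excuses controlled endocrinopathies, which would be redundant if all endocrinopathies were already exempt.
- An exemption for infusion reactions would contradict 4.6.7.

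Context therefore strongly favours *stop at any duration*. The words that would say so are absent.

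**Step 2: does another provision supply the rule?** Protocol 4.6.7 speaks of both infusion and hypersensitivity reactions ("it is unlikely to be immunogenic and induce infusion or hypersensitivity reactions") and names bronchospasm as a manifestation ("it might manifest with fever, chills, rigors, headache, rash, pruritus, arthralgias, hypotension, hypertension, bronchospasm, or other allergic-like reactions"). It can therefore be read to reach hypersensitivity and reaction-related bronchospasm as well. Starting from seven types and widening what counts as cover:

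| Cover accepted elsewhere | Types covered | Types left |
|---|---|---|
| Infusion reactions (4.6.7) | 1 | 7 − 1 = 6 |
| Plus endocrinopathies (partial rule, next bullet) | 2 | 7 − 2 = 5 |
| Plus hypersensitivity and reaction-related bronchospasm (4.6.7) | 4 | 7 − 4 = 3 |
| Plus uveitis, if the conditional Grade 2 rule is extended to Grade 3 | 5 | 7 − 5 = 2 |

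Pneumonitis and neurologic toxicity remain in every row. The Grade 4 rule does not reach Grade 3. Protocol 4.6.2 names Grade 2 non-skin events, Grade 3 skin events and Grade 3 laboratory abnormalities for dose delay, with no specific entry for Grade 3 non-skin clinical events. The SAP sets no discontinuation criteria.

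**Step 3: what limits the risk if a site reads *exempt*?**

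- Protocol 4.6.4 requires pulmonary toxicity to resolve to baseline. Persistent Grade 1 pneumonitis needs a steroid taper of at least 1 month and Medical Monitor approval.
- Protocol 4.6.5.1 requires stopping after an interruption of more than 6 weeks. Prolonged steroid tapers are excepted, but the Medical Monitor must be consulted before restart.
- Protocol 3.5 and 4.6.5.1 both allow a stop on investigator judgment.
- Protocol 5.3.2 requires immediate evaluation of suspected pulmonary toxicity.
- Protocol 4.6.1 and 5.3.2 refer to guidance in the Investigator Brochure.

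These lower the risk. None is an explicit Grade 3 stop rule.

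**Step 4: effect on the analyses.** A qualifying Grade 3 event enters the primary incidence whether or not dosing then stops, so that count is largely unaffected. SAP 7.6.1.2 also tabulates select adverse events leading to discontinuation, and the pneumonitis entries there could depend on which reading a site applied.

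**The case against.** The strongest reply is that *exempt* survives only if the line is read alone. The parent sentence already names all seven types, so as an exemption the sub-bullet would repeat that list and add nothing. It does work only as an instruction to stop without waiting 7 days. On that view the sub-bullet is itself the stop rule, and the count in the working measures lack of duplication rather than lack of a rule. The guidance on pulmonary and neurological toxicity sits in the Investigator Brochure, which is not among the public documents. Harm also needs a site to choose the weaker reading, the restart conditions to be met, and no judgment stop to be applied; the documents record no such misreading. All of this stands as to intent and practical size. It does not supply the missing action, and read literally the sentence gives the wrong one.

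A reader might infer more than the documents support, in three ways.

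- *That 4.6.4 contains a second gap*, because its skin bullet refers to prior Grade 3 and its pneumonitis text does not. The skin bullet does not bar restart after Grade 3; it only withholds permission to resume while Grade 2 skin toxicity persists. It is needed because Grade 3 skin events are delayed under 4.6.2 and fall outside the non-skin stop rule. Once 4.6.5.1 states the stop, a limit on prior pneumonitis grade in 4.6.4 is redundant.
- *That three types are firmly without a rule.* A Grade 3 uveitis would reasonably be handled at least as strictly as the conditional Grade 2 rule requires, so only two types are left under every count.
- *That the primary result is biased.* The primary count does not depend on whether dosing stops after the event.

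**Conclusion.** The point holds as an omitted action in a safety stop rule. The intended meaning is very probably to discontinue at any duration, but the literal text exempts the listed events. Because the literal reading reverses the action, this is more than a clerical slip and should be fixed.

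Size: of the seven listed types, 2 (pneumonitis and neurologic toxicity) have no explicit Grade 3 stop rule elsewhere on any count. The number rises to 6 if only infusion reactions are accepted as covered. The documents give no rates for these events, so the number of subjects cannot be estimated. The gain is in subject safety and consistent site conduct; the existing backstops keep the practical risk limited.

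This rests on three assumptions.

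- The line belongs under the exceptions. The colon ending the parent sentence supports this, though nesting may have been altered in the text extraction; as a free-standing entry the line would simply mean *stop*.
- No words were lost in extraction. No redaction mark appears at that line, but loss cannot be fully excluded.
- Neither the Investigator Brochure nor the unavailable text between 4.1 and the start of 4.6 states the rule. If either does, the risk is smaller, but the sentence in 4.6.5.1 is still incomplete.

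**What to change.** In 4.6.5.1, keep the seven event types in the first sub-bullet, join the last two with *or*, and complete the sentence: *… of any duration requires discontinuation, except endocrinopathies as stated in the next bullet.* Add a cross-reference to 4.6.7 for infusion reactions. The sponsor's medical team should confirm that this is the intent; if any listed type is meant to be exempt, the text should say so for that type and be reconciled with 4.6.7. Send sites a short notice of the clarified rule. Protocol 4.6.4 needs no change.

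The cost is one clause, one cross-reference and a site notice. Sample size, endpoint definitions and planned analyses stay as they are.
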